10.2 Monitoring for AEs

Subjects will be monitored for the occurrence of adverse events at all study visits, including follow up.

Reporting procedures will comply with BIDMC IRB policies; US Federal Regulations (21CFR 312), and ICH Guideline E-6: *Guidelines for Good Clinical Practice*.

Adverse events will be coded and graded according to the NIH/NCI Common Terminology Criteria for Adverse Events version 4.03 (June 2010). All adverse events will be classified on seriousness (mild, moderate, serious), expectedness (expected, non-expected), and relatedness to trial (not related, possibly related, related).

Reporting Serious Adverse Events: All serious adverse events (SAEs) will be reported to the BIDMC IRB, regardless of the determined relationship to the study drug, within the timeframes specified below:

- **Unexpected Fatal or Life-Threatening SAEs** will be reported within one (1) business day of PI awareness. A formal written report (signed by the PI) will be submitted within seven (7) calendar days of PI awareness.
- All other unexpected SAEs will be reported as a formal written report (signed by the PI) within seven (7) calendar days of PI awareness.
- **Expected SAEs:** For all expected SAEs, we will submit a formal, written report (signed by the PI) with fourteen (14) calendar days of PI awareness.

Non-serious AEs will be evaluated by the PI to determine the relationship of the event to the study drug, then reported to the CCI in the timeframe and manner specified below:

- **Related:** Non-Serious AEs determined by the PI to be possibly, probably, or definitely related to the Study (or relationship unknown):

- ✓ Unexpected/related: non-serious AEs that are unexpected and determined to be related to study drug, will be reported in a formal written report (signed by the PI) within fourteen (14) calendar days of PI awareness.
- ✓ Expected/related: non-serious AEs that are expected and determined to be related but which occur with greater frequency than expected, will be summarized for submission on the continuing review progress report at the study's continuing review.
- **Unrelated**: Non-serious AEs determined by the PI to be unrelated to the study:
 - ✓ Unexpected /unrelated: non-serious AEs that are unexpected and determined to be unrelated which occur with greater frequency than expected, will be summarized for submission on the continuing review progress report at the study's continuing review

IND Safety Reporting

In compliance with federal regulation (21 CFR 312), safety reports will be submitted to the FDA (via submission of an IND Safety Report) when an event meets all of the following criteria:

- Suspected adverse reaction (reasonable possibility of relationship with study drug)
- Serious
- Unexpected

Fatal or life threatening events will be reported as soon as possible but no later than 7 calendar days from time the Sponsor becomes aware.

Serious and unexpected adverse events Adverse Events will be reported as soon as possible but no later than 15 days from the time the Sponsor becomes aware.

Reporting to Prometheus

A copy of any SAE report submitted to the BIDMC IRB, Sponsor and FDA will be sent to Prometheus Laboratories. If interleukin-2 is a suspect or co-suspect drug reported on the FDA Form 3500A MedWatch Report, a copy of the FDA Form (3500A MedWatch Report) will also be sent to Prometheus Laboratories as a courtesy. Reports to Prometheus will be sent to Drug Safety and Pharmacovigilance at Prometheus Laboratories Inc. All contact information will be included in the Report.

Drug Safety Email: [contact]

Drug Safety [contact]

Avoiding bias in laboratory testing:

Blood specimens drawn and processed for immunological testing will be de-identified, logged and labeled prior to transfer to the central laboratory. Specimen labeling system will be designed such that the lab staff will not be aware of the visit sequence of the specimen in relation to pre vs post treatment status.

Independent Medical Monitor (IMM)

The PI has named an Independent Medical Monitor who is familiar with the agent and with the patient population, [name], PhD, Professor of Medicine, Harvard Medical School. [name] is a world leader in the study of vascular and immune cell ectonucleotidases in pathophysiology and transplantation. He is also a prominent investigator in liver and gastrointestinal diseases.

The IMM will review all SAE reports sent to the BIDMC IRB, Sponsor and FDA in real time. The IMM will also review aggregate data as they are available.

Routine Monitoring: To further ensure the study is conducted and documented in accordance with the investigational plan, applicable regulations and good clinical practices, routine monitoring will be conducted by the Transplant Institute's Clinical Research Associate or other qualified designee in fulfillment of the Sponsor's obligation for monitoring. Monitoring activities will include:

- Review of essential documents in the regulatory binder for completeness and currency;
- Inspection of every (100%) informed consent form to assure that correct versions are used; that the names of subject and consenter are legible; that forms are properly signed and dated by subject and consenting physician investigator; and documentation is available to document consent procedures.
- Verification that every enrolled subject meets eligibility criteria;
- Review of a minimum of 10% of case report forms entered to source verify accuracy and completeness with specific attention to ...
 - ✓ Dose modifications
 - ✓ Adverse events, concomitant medications and intercurrent illnesses
 - ✓ Missed study visits, procedures, labs, etc
 - ✓ Drop out and withdrawals
- Review of all regulatory reporting
- Reporting findings to Sponsor/Investigator.

Table 1: Study Visits Schedule and Procedures

	Visit	Screening and Baseline		Treatment to Week 4					Follow-up to Week 36		
		Screening	Baseline Day 1	Day 3	W1	W2	W3	W4	W8	W12	W36
Study Procedures:	Visit #	1	2	3	4	5	6	7	8	9	10
Informed Consent		✓									
Full Physical Exam & Medical History		✓									✓
Limited Physical Exam & Medical History			✓	✓	✓	✓	✓	✓	✓	✓	✓
Vital Signs		✓	✓	✓	✓	✓	✓	✓	✓	✓	✓
Electrocardiogram (ECG)		✓			✓	✓	✓	✓			
Fibroscan		✓ ¹									
Study Blood Tests:											
Pregnancy test (for women of child bearing potential)		✓							✓	✓	✓
CBC with Differential			✓	✓	✓	✓	✓	✓	✓ ⁴	✓ ⁴	✓ ⁴
Liver panel (AST, ALT, AP, Total Bilirubin, Albumin)		✓ ²	✓	✓	✓	✓	✓	✓	✓ ⁴	✓ ⁴	✓ ⁴
Kidney panel (Na, K, Cl, CO2, Creatinine, Glucose, Ca)		✓ ²	✓	✓	✓	✓	✓	✓	✓ ⁴	✓ ⁴	✓ ⁴
Viral hepatitis and autoimmunity panels (HBVsAg, HCVAb, ANA, ASMA IgG)		✓ ³									
Immunosuppression drug level			✓						✓ ⁴	✓ ⁴	✓ ⁴
Immune cell counts			✓			✓			✓	✓	✓
IL-2 Blood level			✓		✓	✓	✓	✓	✓	✓	✓
T-cell exhaustion markers (only at baseline)			✓								
DSA (pre and post IL-2 treatment)			✓						✓		
Samples anti IL2 antibody testing			✓						✓		✓

¹ Only if a fibroscan or a liver biopsy was not completed for standard of care within the last 12 months

² Only if liver panel or kidney panel was not collected for standard of care within the last month

³ Only if viral and autoimmunity tests not completed for standard of care within past 6 months

⁴ Obtained as part of standard of care

B. Statistical Considerations

Sample Size Justification: This is a pilot study to determine the efficacy and safety of very low dose IL-2 administration in a select group of liver allograft recipients. Investigators will consent as many as 12 subjects into the screening phase in order to treat not more than 10 patients from the BIDMC Transplant Institute's Liver Transplant Program.

The primary endpoint for the trial is the percent change in absolute numbers of regulatory T cells (Tregs) from pre-treatment baseline to end of treatment, i.e. the week 4 treatment visit.

For IL-2 to be clinically viable, we would require evidence that 60-80% of participants experience a biological response defined as a 2 fold increase in absolute number of Treg cells from baseline. Less than 50% of responding participants would be an unacceptable low response. The success of IL-2 will be defined based on a one sided 95% confidence interval (CI). The CI for a 0.80 response rate with 10 subjects would be 0.59-1.00 enabling exclusion of a response rate of 0.50.

Data Analysis: Differences in absolute numbers of circulating endogenous Treg cells from baseline to end of treatment will be compared using standard descriptive statistics and paired t-tests.

C. Subject Selection

Study subjects will be identified from the BIDMC Transplant Institute Liver Transplant Program by hepatologist [name] (Medical Director of the Liver Transplant Program) and surgeon [name] (Surgical Director of the Liver Transplant Program).

Inclusion criteria:

1. Adult liver transplant recipients 2-4 years post transplantation
2. Male or female, age \leq 65 years old
3. Stable dosage of immunosuppressant therapy for 1 month prior to study.

Exclusion criteria:

1. Recipient of multiple transplants (including solid organ, stem-cell, and bone marrow)
2. Serum liver panel (ALT, AST, Alkaline Phosphatase and Total Bilirubin) $> 2 \times$ ULN,
3. Serum creatinine $> 1.5 \times$ ULN,
4. eGFR of < 40 ml/min,
5. Detectable hepatitis viral load,
6. Abnormal ECG with clinically significant findings per study physician's judgement,
7. Active infection,
8. Presence or history of autoimmunity disorders,
9. Evidence of allograft rejection,
10. Liver biopsy or fibroscan evidence of advanced stage liver fibrosis ($>$ Stage 2 Fibrosis),
11. Presence or history of cardiac or pulmonary disease,
12. Pregnant or nursing (lactating) women,
13. Presence or history of seizure disorder,
14. Health condition precludes participation in trial at study physician's judgment,
15. Inability to give consent.

Male and female participants of all racial distributions are eligible for this study. Participation is limited to subjects who are less than 4 years post-transplant and less than or equal to 65 years old as individuals who are further out from transplant and older in age are likely to have a higher chance of spontaneous operational tolerance and less likely to need pharmacologic intervention to achieve tolerance.

B4. POSSIBLE BENEFITS

It is not possible to predict whether subjects will benefit directly from participation in this study. Regardless, participation may help others in the future as a result of knowledge gained from the research.

Demonstration that very low dose, subcutaneous IL-2 can induce endogenous Treg cell expansion will allow further study of IL-2 mediated operational tolerance in liver allograft recipients. Future studies will consider reducing or withdrawing systemic IS in a cohort of patients who respond to IL-2 expansion of Tregs.

This preliminary study may identify patients who are IL-2 responsive and possible candidates for future studies of IS reduction. Successful induction of tolerance and withdrawal of IS would decrease the morbidity associated with lifelong use of IS agents for control of organ rejection.

B5. POSSIBLE RISKS AND ANALYSIS OF RISK/BENEFIT RATIO

Risk of Interluekin-2 (Proleukin, IL-2):

IL-2 is approved as a treatment for metastatic renal cell carcinoma and metastatic malignant melanoma. It is most commonly administered to cancer patients as a high-dose intravenous treatment regimen. For these cancer indications, dosing guidelines prescribe a three times per day intravenous infusion of 600,000 International Units (IU) per kilograms of body weight (e.g. dose for a person weighing 82kg is 49.2 million IU x 3 infusions/day = 147.6 million IU per day, compared to a daily dose for the same person for the proposed protocol would = 1.95 million IU/day) Significant side effects are expected with the high dose IV regimen for cancer treatment though they are reversible once treatment is stopped. Type and severity of side effects is dose dependent.

The drug manufacturer Novartis has conducted 7 Phase I/II clinical trials in 235 patients with a variety of doses and schedules using subcutaneous IL-2. Dosages have ranged from 2 million IU per day to 9 million IU per day. The study populations included metastatic renal cell carcinoma, advanced malignancy, and chronic lymphocytic lymphoma. In these trials, the following adverse events were recorded:

- Pyrexia (fever) – 77%
- Rigors (shivering) – 68%
- Asthenia (tiredness) – 49%
- Anorexia (loss of appetite) – 54%
- Nausea – 50%
- Vomiting – 49%
- Diarrhea – 40%
- Headache – 35%
- Dry skin – 25%
- Rash – 24%
- Injection site inflammation – 24%
- Dyspnea (shortness of breath) – 24%
- Injection site reaction – 24%
- Cough – 23%
- Myalgia (muscle pain) – 23%
- Insomnia – 21%
- Hypokinesia (muscle rigidity) – 20 %
- Dizziness – 18%
- Abdominal pain – 16%
- Injection site pain – 14%

- Depression – 11%
- Pruritus (itchiness) – 10%
- Oliguria (decrease in urine production) – 9%
- Confusion – 8%
- Hypotension (low blood pressure) – 7%
- Anxiety – 6%
- Increased serum creatinine – 4%
- Tachycardia (increased heart rate) – 3%
- Gastrointestinal bleeding – 2%
- Arrhythmia (unusual heart beat) – 1%
- Myocardial infarction (heart attack) – <1%
- Kidney failure – <1%

The most common serious adverse event associated with **high dosage, IV administered IL-2** is capillary leak syndrome where capillary permeability increases and serum proteins and fluids move to the extravascular space. In subcutaneous administration of IL-2, capillary leak syndrome is much less frequent and less severe. In the Novartis clinical trials of **subcutaneous IL-2**, no cases of pulmonary edema were recorded. Peripheral edema occurred in 14% of patients and unspecified edema occurred in 11% of patients.

IL-2 has not been approved for use for the indication being tested in this study. In this study we will test the efficacy and safety of low dose IL-2, i.e., 0.3 million IU per square meter body surface area (BSA) given once a day in subcutaneous injections, to liver transplant patients over a 4 week period of time to measure the effect on the number of peripheral Treg cells.

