This pilot trial will treat up to 10 liver transplant recipients who are ≤65 years of age, a minimum of 2 years but no more than 4 years post primary liver transplantation for non-autoimmune conditions, have had no evidence of transplant rejection, and have no current evidence of liver allograft dysfunction or viral hepatitis.

Study objectives include (1) determine the efficacy of the administration of low dose IL-2 to promote Treg cell expansion; (2) assess the safety and efficacy of low dose IL-2 in a liver transplant recipient cohort; (3) investigate the percent change of peripheral blood Treg cells and change in phenotype and function of Treg cells in response to low dose IL-2 in a liver transplant recipient cohort.

Study Scheme:

Study Procedure:

Screening (S0):

After obtaining informed consent the following screening procedures will be completed:

- Full history and medical record review
- Physical examination including height and weight
- Vital signs (blood pressure, heart rate and temperature)
- Blood (approximately 20 milliliters) will be drawn for
 - ✓ liver function panels (AST, ALT, ALP, Bilirubin, Albumin) and kidney function panels (Na, K, Cl, CO₂, Creatinine, Glucose, Ca) if not previously obtained within 1 month of screening
 - ✓ viral hepatitis and autoimmune panels (HBV sAg, HCV Ab, ANA, ASMA IgG) if not previously obtained within 6 months of screening
 - ✓ serum pregnancy test for women of child bearing potential (WOCBP)
- Fibroscan if liver biopsy/fibroscan results not obtained within 1 year of screening
- ECG if not obtained within 3 months of screening

Subjects with liver panel results <2xULN, serum creatinine <1.5 ULN; no evidence of viral hepatitis or

autoimmunity, no evidence of pregnancy, absence of advanced liver fibrosis, no history of seizure disorder and no evidence of cardiac disease will proceed with the study (see Inclusion/Exclusion criteria in section below).

Baseline/Treatment Visit Day 1 (W0):

Subjects will return to clinic to complete baseline measures and begin study treatment:

- Review of any new health problems, current medication and vital sign measures;
- Blood draw (approximately 35 milliliters) for
 - ✓ CBC with differential,
 - ✓ liver and kidney function panels,
 - ✓ immune cell counts ,
 - ✓ T cell exhaustion phenotyping,
 - ✓ serum IL-2 levels,
 - ✓ CNI trough levels,
 - ✓ presence of donor specific antibodies (DSAs)
 - ✓ presence of anti-IL-2 antibodies

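### The 0.59 lower limit quoted for 8/10 responders is a normal-approximation figure that does not hold 95% at n = 10; small-sample limits run from 0.49 to 0.55, and the plan fixes neither method nor responder count

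*Combined protocol and SAP*

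**What the plan says.** Section B3.B (Statistical Considerations, Sample Size Justification) sets a formal criterion: "The success of IL-2 will be defined based on a one sided 95% confidence interval (CI"). A response is "defined as a 2 fold increase in absolute number of Treg cells from baseline". The target is stated as "we would require evidence that 60-80% of participants experience a biological response", and the floor as "Less than 50% of responding participants would be an unacceptable low response". The only numerical support for the sample size, and the only illustration of how success is judged, is "The CI for a 0.80 response rate with 10 subjects would be 0.59-1.00 enabling exclusion of a response rate of 0.50".

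No interval method is named and no minimum number of responders is given. The Data Analysis paragraph does not fill the gap: Treg differences "will be compared using standard descriptive statistics and paired t-tests", and no binomial interval or test is mentioned.

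Ten is a ceiling, not a fixed number. B3.B speaks of consenting up to 12 "in order to treat not more than 10 patients", and the design overview in B3.A says "This pilot trial will treat up to 10 liver transplant recipients".

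**The concern.** A normal approximation for a proportion is unreliable with 10 subjects and an observed rate near 1. If 0.59 comes from that formula, the margin above 0.50 looks wider than the data would support. The statement that 0.50 is excluded then depends on a choice of method that the plan does not record.

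Two things are at stake. The sentence is the sole justification for n = 10, so an optimistic limit overstates what the trial can show. And with neither method nor count fixed in advance, a borderline result could be called success or failure according to the interval chosen after the data are seen. The result has consequences: the objectives say that, if treatment is safe, well tolerated and expands Tregs significantly, a follow-up study with withdrawal of immunosuppression will be proposed.

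**Working it through.** **Inputs (all from B3.B).** One-sided 95% level, so z = 1.645; n = 10; observed rate 0.80, that is x = 8; reference rate 0.50; target range 0.60-0.80. Success is read as a lower limit above 0.50, as in the worked example.

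**1. Reproduce the plan's figure.** Wald limit: 0.80 − 1.645 × √(0.8 × 0.2 / 10) = 0.80 − 1.645 × 0.1265 = 0.592. This matches 0.59. For 7/10 the same formula gives 0.462, so the implied rule is at least 8 of 10.

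**2. Does this limit hold 95%?** Coverage is the binomial probability that the limit does not exceed the true rate. The Wald limits are 0.592 for 8/10, 0.744 for 9/10 and 1.00 for 10/10.
- True rate 0.50: missed if X ≥ 8, probability 0.0547; coverage 94.5%.
- True rate 0.70: missed if X ≥ 9, probability 0.1493; coverage 85.1%.
- True rate 0.80: missed if X = 10, probability 0.8^10 = 0.1074; coverage 89.3%.

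Over an even grid of true rates from 0.60 to 0.80, mean coverage is 89.2% for Wald (minimum 76.9%), 94.1% for Jeffreys, 95.2% for mid-P, 95.4% for Wilson and 98.4% for exact.

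**3. Small-sample lower limits for 8/10.**
- Jeffreys: 5th percentile of Beta(8.5, 2.5) = 0.548.
- Wilson: [0.8 + z²/20 − z√(0.016 + z²/400)] / (1 + z²/10) = 0.541.
- Mid-P: the p that solves P(X > 8) + ½P(X = 8) = 0.05 is 0.533.
- Exact (Clopper-Pearson): 5th percentile of Beta(8, 3) = 0.493.

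The first three exclude 0.50, by 3 to 5 points. The exact limit does not. The plan's 0.592 exceeds them by 0.592 − 0.548 = 0.044 up to 0.592 − 0.493 = 0.099.

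**4. Error and chance of success of the possible rules (exact binomial).**

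| Rule | Error at 0.50 | Chance of success at 0.60 | at 0.70 | at 0.80 |
|---|---|---|---|---|
| ≥ 8 of 10 | 56/1024 = 5.47% | 0.167 | 0.383 | 0.678 |
| ≥ 9 of 10 | 11/1024 = 1.07% | 0.046 | 0.149 | 0.376 |

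The 8/10 error is 4.80% at a true rate of 0.49. It exceeds 5% only from 0.493 upwards.

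**5. Fewer than 10 treated.**
- n = 9: 7/9 passes by Wald (0.550), Jeffreys (0.508) and Wilson (0.504) and fails by mid-P (0.492) and exact (0.450). Its error is 46/512 = 9.0%, and its chance of success at 0.80 is 0.738. Requiring 8/9 (exact limit 0.571) gives an error of 10/512 = 2.0% and a chance of 0.436.
- n = 8: all five methods require 7/8 (Wald for 6/8 is 0.498; exact for 7/8 is 0.529). The error is 9/256 = 3.5%, and the chance at 0.80 is 0.503.

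**The case against.** The strongest reply is that nothing has been miscalculated and that the decision at n = 10 barely changes. The Wald sum is correct. Wilson, Jeffreys and mid-P all agree that 8/10 excludes 0.50; the dissenters are the exact limit, which is conservative, and the continuity-corrected Wilson limit (0.490). At the reference rate of 0.50, Wald coverage is the same 94.5% as for those three methods, because they share the 8/10 threshold. The poor coverage at 0.70 and 0.80 affects how the interval is reported, not the test against 0.50. The worked example also points to Wald, since no other variant tried rounds to 0.59, and it states the verdict for 8/10. Finally, this is a pilot, and subjects withdrawn from treatment complete their remaining visits, which helps keep all 10 evaluable.

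Most of this stands as a limit on size. At n = 10 the excess over 5% is about half a percentage point, and a mid-P rule would leave the decision unchanged. Mid-P is not perfect either: its coverage falls to 90.0% at worst within 0.60-0.80, and only the exact limit keeps 95% throughout.

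It does not remove the point. The printed limit still overstates the evidence by 4 to 10 points. A method that must be inferred from one rounded figure is not a specified method. And if it is inferred to be Wald, following it with 9 treated passes 7/9 at a 9.0% error. Pilot status excuses a small sample, not an open success criterion where the plan itself chose a formal 95% interval.

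**Conclusion.** The concern holds and should be fixed. The stated 0.59 is a Wald limit that does not keep its nominal 95% at n = 10. Defensible small-sample limits for 8/10 lie between 0.49 and 0.55, and whether 0.50 is excluded depends on a method the plan does not name. The implied 8/10 rule has a true one-sided error of 5.47%, a minor excess. The larger exposure is below 10 subjects, where at n = 9 the methods disagree on 7/9 and the plan's own formula accepts a 9.0% error.

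This rests on three assumptions: success means a lower limit above 0.50; responses are independent with a common rate; and the denominator is the number treated. The n = 9 and n = 8 figures matter only if fewer than 10 are treated, which the plan permits but does not forecast.

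**What to change.** Name one small-sample interval in advance, replace 0.59-1.00 with its value, drop the unqualified claim that 0.50 is excluded, and state the responder count with its operating characteristics. Either option below is adequate if fixed before the data are seen; the choice is the sponsor's.

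**Option A (keeps 8/10).** Suggested text:

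> Success is declared if the mid-P one-sided 95% lower limit exceeds 0.50. With 10 treated subjects this requires at least 8 responders (8/10: mid-P interval 0.53-1.00; exact lower limit 0.49). The one-sided error at a true rate of 0.50 is 5.5%, and the chance of success is 0.17, 0.38 and 0.68 at true rates of 0.60, 0.70 and 0.80. With 9 treated at least 8 responders are required (error 2.0%), and with 8 treated at least 7 (error 3.5%).

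**Option B (error at or below 5%).** Use the same text with the exact limit. For 8/10 the interval is then 0.49-1.00 and does not exclude 0.50. Success requires at least 9/10 (0.61-1.00; error 1.1%; chance of success 0.05, 0.15 and 0.38), 8/9 or 7/8.

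**Cost.** A few sentences, with no extra patients or procedures, and a less favourable printed limit. Option A leaves the 8/10 decision unchanged but discloses the 5.5% error. Option B lowers the chance of success at a true rate of 0.80 from 0.68 to 0.38, and at 0.70 from 0.38 to 0.15. If only 9 are treated, requiring 8/9 instead of 7/9 lowers the chance at 0.80 from 0.74 to 0.44 under either option.

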NCT Number: NCT02739412

Official Title: Efficacy of Low Dose, SubQ Interleukin-2 (IL-2) to Expand Endogenous Regulatory T-Cells in Liver Transplant Recipients

Document Type: Protocol with Statistical Analysis Plan

Document Date: 09/07/2017

PART B STUDY DESCRIPTION

TITLE OF PROTOCOL	Efficacy of Low Dose, Subcutaneous Interleukin-2 (IL-2) to Expand Endogenous Regulatory T-Cells in Liver Transplant Recipients
Principal Investigator	[name]

B1. PURPOSE OF PROTOCOL

The primary objectives of this pilot study are:

1. To assess the efficacy of very low dose subcutaneous interleukin-2 (IL-2) to promote regulatory T cell (Treg) expansion in a cohort of liver transplant recipients with stable graft function, no active or history of auto-immune diseases, no evidence of allograft rejection, no current evidence of viral hepatitis, and no advanced liver graft fibrosis.
2. To assess the safety and tolerability of very low dose IL-2 in a liver transplant recipient cohort.

Secondary objectives:

1. To investigate the percent change of peripheral blood Treg cells and change in phenotype and function of Treg cells in response to very low dose IL-2 in a liver transplant recipient cohort.
2. To identify patients who are IL-2 responsive and thereby potential candidates for withdrawal of immunosuppression. This pilot study will not involve withdrawal of immunosuppression (IS), however if it is determined that low dose IL-2 is safe, well tolerated, and results in significant expansion of Treg cells, then subsequently a follow-up study of IL-2 expansion of Treg cells followed by IS withdrawal will be proposed.
3. Assess short term impact of study treatment on subject's DSA status, i.e. change in DSA titers or development of de novo DSA.

Exploratory Objective:

1. Establish baseline phenotypic values for T cell exhaustion in the trial cohort.
2. Determine if IL-2 treatment results in development of IL-2 antibodies in the study population

B2. SIGNIFICANCE AND BACKGROUND FOR THE STUDY

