- Review standard of care lab results for
 - ✓ CBC with differential,
 - ✓ liver and kidney function panels,
 - ✓ CNI trough levels,
- Blood draw (approximately 20 milliliters) for study labs
 - ✓ Immune cell counts (Weeks 8 and 12)
 - ✓ serum IL-2 levels (Weeks 8 and 12)
 - ✓ serum pregnancy test for WOCBP (Weeks 8 and 12).
 - ✓ anti-IL-2 antibodies (Week 36)

Dosage Reduction and Treatment Withdrawal

The dose of IL-2 may be reduced by half to 0.15 million IU /m² daily if a subject experiences untoward side effects. If symptoms improve, the dose may be re-escalated to target. If symptoms persist, the dose frequency may be reduced to every other day administration or the Investigator may discontinue study treatment.

Study treatment will be discontinued in the presence of any of the following circumstances:

- ✓ Subject withdraws consent
- ✓ Life threatening anaphylactic reaction to IL-2
- ✓ Life threatening infection on IL-2
- ✓ The Investigator may discontinued study treatment in the presence of other clinically significant findings including abnormal ECG, blood panel results >2x ULN and/or other signs of significant toxicities.

Subjects who are withdrawn from treatment will complete remaining study visits and continue to receive follow-up care from his/her BIDMC transplant Hepatologist.

Standard of Care Maintenance Immunosuppression: Eligible patients must be receiving stable dosing of immunosuppressant therapy for a minimum of 1 month prior to study enrollment. Maintenance immunosuppression is customize to the patient but typically, stable liver transplant patients at 2-4 year post transplant who are otherwise eligible to enroll into this trial would be taking tacrolimus (target 12 hour trough goal of 4-6ng/mL) with or without mycophenolic acid (as mycophenolate mofetil or mycophenolate sodium) at a dose between 500-1000mg twice a day.

Safety Monitoring

The PI is ultimately responsible for protecting the rights, safety and welfare of subjects enrolled into the trial. Study visits will be conducted weekly during the treatment phase of the trial; post treatment follow-up visits will be conducted at week 8 and 12. The PI will review all safety parameters including clinical safety laboratory assessments within 48 hours of completion of the measure. Clinical laboratory values that fall outside of the pre-specified safety ranges will be brought to the PIs attention the day the reports are final to assess clinical significance.

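### The Data Analysis paragraph tests raw differences in Treg counts, which estimate neither the percent-change primary endpoint nor the responder rate that defines success; the implied responder CI also exceeds its nominal 5% error at most sample sizes checked

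*Combined protocol and SAP*

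**What the plan says.** Everything on this point is in section B3.B, Statistical Considerations, spread over two short paragraphs.

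- **Primary endpoint (Sample Size Justification):** "The primary endpoint for the trial is the percent change in absolute numbers of regulatory T cells (Tregs) from pre-treatment baseline", measured to the week 4 visit.
- **Success rule (same paragraph):** a responder is a subject whose absolute Treg count rises 2-fold, and a response rate below 50% is unacceptable. "The success of IL-2 will be defined based on a one sided 95% confidence interval (CI". The worked case is: "The CI for a 0.80 response rate with 10 subjects would be 0.59-1.00 enabling exclusion of a response rate of 0.50". The interval method is not named.
- **Data Analysis:** this is a single sentence. Differences in "absolute numbers of circulating endogenous Treg cells from baseline to end of treatment will be compared using standard descriptive statistics and paired t-tests". It mentions neither percent change nor the responder proportion.
- **Number treated:** ten is a ceiling. Section B3.B says "in order to treat not more than 10 patients", and the design overview in B3.A says "This pilot trial will treat up to 10 liver transplant recipients".

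No other section gives an analysis method for percent change or for the responder proportion.

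**The concern.** The plan contains three quantities: percent change (the primary endpoint), the proportion of subjects who double (the success criterion), and the mean raw difference in counts (the named test). The third is neither of the first two. A rise of 20 cells is +100% for a subject starting at 20 and +25% for a subject starting at 80, yet both contribute the same amount to the raw difference. The raw mean therefore leans towards subjects with high baselines and gives no estimate or interval for percent change.

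A second issue arises when the responder rule is carried into the analysis. It is worked out only for 10 subjects, by a method that has to be inferred. In samples this small, the chance of declaring success at the response rate the plan wants to exclude need not be the nominal 5%, and it moves with the number treated. At stake is whether the report contains a usable estimate of the primary endpoint, and whether the stated confidence level describes the real risk of a false success.

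**Working it through.** **1. Reproducing the stated interval.** Inputs from B3.B: response rate 0.80, n = 10, one-sided 95% (z = 1.645).

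Wald lower limit = 0.80 − 1.645 × √(0.80 × 0.20 / 10) = 0.80 − 1.645 × 0.1265 = 0.592. This matches the stated 0.59. Other methods for 8/10 do not: one-sided Wilson gives 0.541, two-sided Wald 0.552 and one-sided exact (Clopper-Pearson) 0.493. The plan's figure therefore identifies one-sided Wald. Under the exact method, 8/10 does not exclude 0.50.

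**2. Required responders and true error by number treated.** For each n, the bar is the smallest count whose one-sided 95% lower limit exceeds 0.50. False success is the binomial probability of reaching that bar at a true rate of 0.50, for example (45 + 10 + 1)/1024 = 5.5% for at least 8/10 and (36 + 9 + 1)/512 = 9.0% for at least 7/9.

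| Treated | Wald or Wilson bar (Wald / Wilson limit) | False success at 0.50 | Success at 0.80 | Exact bar (limit) | False success at 0.50 | Success at 0.80 |
|---|---|---|---|---|---|---|
| 10 | 8 (0.592 / 0.541) | 5.5% | 67.8% | 9 (0.606) | 1.1% | 37.6% |
| 9 | 7 (0.550 / 0.504) | 9.0% | 73.8% | 8 (0.571) | 2.0% | 43.6% |
| 8 | 7 (0.683 / 0.589) | 3.5% | 50.3% | 7 (0.529) | 3.5% | 50.3% |
| 7 | 6 (0.640 / 0.548) | 6.3% | 57.7% | 7 (0.652) | 0.8% | 21.0% |

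One responder fewer fails under Wald at 10 and at 8: 7/10 gives 0.462 and 6/8 gives 0.498.

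**3. Raw test against log-ratio test.** The documents give no Treg values or SD, so these inputs are assumed: n = 10, lognormal baseline with CV 30–50%, log fold change normal with mean ln 2 (median doubling) and SD 0.4–0.7, two-sided 5% test.

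- *Log ratio.* The one-sample t-test on log(week 4/baseline) does not depend on the baseline distribution. Its noncentrality is 0.693 × √10 / SD, which is 5.48 at SD 0.4 and 3.13 at SD 0.7. With 9 degrees of freedom, power against no change is 99.8% and 79.5%.
- *Raw difference.* By simulation (200,000 trials per scenario), power is 96.0% (SD 0.4) to 65.7% (SD 0.7) at CV 50%, and 98.6% to 72.0% at CV 30%.

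**4. The two analyses answer different questions.** Assume baselines of 20, 25, 30, 35, 40, 45, 50, 60, 70, 80 and fold changes of 1.5, 1.3, 1.6, 1.4, 1.35, 1.55, 1.45, 1.3, 1.6, 1.4. The mean difference is 20.3 cells (95% CI 12.8–27.8), t(9) = 6.11, p = 0.0002. Mean percent change is 44.5%, and the geometric mean fold change is 1.44 (95% CI 1.36–1.52). No subject doubles, so responders are 0/10. The t-test correctly finds an increase, and the responder rule correctly finds that it is not a doubling.

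**The case against.** The strongest reply is that the plan already settles what counts. It says success is defined by the responder CI, gives the responder definition and the unacceptable rate, and works a case. Doubling is a percent change of at least 100%, so the responder analysis is itself a dichotomised analysis of the endpoint, and descriptive statistics could include percent change. The Wald method can be recovered from 0.59 and applied at any n. In a single-arm pilot of at most 10, the rest is drafting.

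Much of this stands, and it rules out several stronger readings:

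- *That the t-test decides success, or that the plan leaves the ranking open.* The documents do not support this. The success rule is explicit and nothing competes with it.
- *That the raw t-test has a very high false-positive rate.* At a median doubling (true responder rate 0.50), the raw test is significant in 66–99% of simulated trials, while 8/10 or more responders occurs in 5.5%. But the t-test's null of no change is false there, so rejecting it is right. The log-ratio test diverges from the responder rule at least as often, being significant with fewer than 8/10 responders in 74–94% of trials. The contrast shows two different questions and is not an error rate.
- *That the follow-up condition, "results in significant expansion of Treg cells, then subsequently a follow-up study of IL-2 expansion of Treg cells", means a significant t-test.* The text does not say so. It describes when a later study would be proposed, alongside safety and tolerability.
- *That withdrawals leave the week 4 count undefined.* The treatment-withdrawal text says "Subjects who are withdrawn from treatment will complete remaining study visits", so no such fault is shown.

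What the reply does not remove is that continuous percent change, the declared primary endpoint, has no stated scale, estimator or interval, and the one named test is on another scale. Recovering the Wald method also exposes its error rate rather than curing it.

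**Conclusion.** The concern holds in limited form. The named inferential test does not analyse the stated primary endpoint. The responder rule, which does govern success, rests on an unnamed interval whose true one-sided error at a response rate of 0.50 is above the nominal 5% at three of the four sample sizes checked (10, 9 and 7) and below it at 8. The excess is small at the planned maximum and larger at 9.

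The interval limits and binomial rates need no assumption beyond independent subjects and a boundary of 0.50. The power gain from the log scale rests on assumed lognormal data and should be read as indicative. The argument for the log ratio is chiefly that it estimates the endpoint. This should be corrected, but it does not invalidate the design or its success criterion.

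**What to change.** Replace the Data Analysis sentence with text to this effect: *The primary endpoint is analysed as log(week 4/baseline absolute Treg count) and reported as the geometric mean fold change and the matching percent change, each with a 95% CI. Any paired t-test on raw differences is supportive. Success is decided by the proportion of subjects with a ratio of at least 2, using the one-sided 95% CI against 0.50 by the [named] method. The required number of responders and the false-success rate at 0.50 are tabulated by number treated.*

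The interval method is the sponsor's choice. Wald (implied by 0.59) and Wilson keep the bars at 8/10, 7/9, 7/8 and 6/7, with the error rates shown above. Exact needs 9/10, 8/9, 7/8 and 7/7 and keeps error below 5%, but at 10 subjects it lowers the chance of success at a true rate of 0.80 from 67.8% to 37.6%. It would also require the 0.59 statement to be rewritten.

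Two additions are optional: a rule for a missing week 4 count, and a sentence linking the follow-up condition in the B1 and B2 secondary objectives to the responder rule.

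The cost is a slightly longer analysis paragraph and a four-row table, extended if fewer than 7 are treated. No new data, visits or subjects are needed.
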